**AMGEN®** 

Protocol Number: 20170646

Date: 25 August 2020 Page 13 of 35

The overall study design is described by a study schema in Section 1.2 of the protocol. The endpoints are defined in Section 2.1.

## 3.2 Sample Size

Approximately 20 subjects will be enrolled in this study with at least 6 DLT evaluable subjects in each cohort. With 6 evaluable subjects in 1 cohort, there is an 82% chance of observing at least 1 DLT if the true DLT rate is 25%. For cohort 1, at least 10 subjects will be dosed through study day 28.

## 3.3 Adaptive Design

Early stopping for safety rule is specified in Section 7.1.

### 4. Covariates and Subgroups

### 4.1 Planned Covariates

This phase 1 study has no prespecified covariates.

# 4.2 Subgroups

This phase 1 study has no prespecified subgroups.

### 5. Definitions

#### 5.1 General Definitions

### Age at Enrollment

Subject age at enrollment will be collected in years in the clinical database.

### Investigational Product (IP)

The term 'investigational product' is used in reference to AMG 330 in combination with pembrolizumab.

Amgen IP: refers to AMG 330 and Non-Amgen IP: refers to Pembrolizumab.

## Cumulative Dose of AMG 330, Pembrolizumab

AMG 330: The cumulative dose in microgram (µg) is defined as the following with summation over infusions:

(duration of infusion (days) for each dose received × dose received [µg/day])

Protocol Number: 20170646

**Date:** 25 August 2020 Page 14 of 35

Pembrolizumab: The cumulative dose in milligram (mg) is defined as the following with summation over infusions:

\( \) (number of infusion for each dose received × dose received [mg])

Cumulative dose will be calculated within a cycle and across all cycles.

## Bazett-corrected QT Interval (QTcB)

The Bazett correction will be calculated from the investigator reported QT (msec) and RR interval (msec), as follows: QTcB=QT/ (RR/1000)1/2.

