8.2.4.2 Electrocardiograms (ECGs)

Subject must be in supine position in a rested and calm state for at least 5 minutes before electrocardiogram (ECG) assessment is conducted. If the subject is unable to be in the supine position, the subject should be in most recumbent position as possible. ECGs should be performed in a standardized method, in triplicate, and run consecutively (all 3 ECGs should be completed within a total of 5 minutes from the start of the first to the completion of the third), prior to blood draws or other invasive procedures. Each ECG must include the following measurements: QRS, QT, QTc, RR, and PR intervals.

- 3 baseline ECGs collected ≥ 30 minutes apart, with each baseline ECG in triplicate run consecutively (all 3 ECGs should be completed within a total of 5 minutes from the start of the first to the completion of the third) (total 9 ECGs)
- Triplicate ECGs at time points after dosing

Baseline is defined as pre-dose on cycle 1 day 1. The investigator or designated site physician will review all ECGs. ECGs will be transferred electronically to an ECG central reader for analysis per Amgen instructions. Once signed, the original ECG tracing will be retained with the subject's source documents. At the request of the sponsor, a copy of the original ECG will be made available to Amgen or designee. Standard ECG machines should be used for all study-related ECG requirements.

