# 2. Objectives, Endpoints and Hypotheses

# 2.1 Objectives and Endpoints

Ob	jectives	Endpoints	
Pri	mary		
•	Evaluate the safety and tolerability of AMG 330 administered in combination with pembrolizumab in subjects with relapsed or refractory acute myeloid leukemia (R/R AML)	
 
Dose-limiting toxicities (DLTs)
 
Treatment-emergent adverse events (TEAEs), treatment-related adverse events (TRAEs), and changes in vital signs, electrocardiograms (ECGs), and clinical laboratory tests
 
	
Se	condary		
•	Evaluate the anti-leukemia activity of AMG 330 administered in combination with pembrolizumab in R/R AML patients	Responses to treatment with AMG 330 administered in combination with pembrolizumab. Response is defined as any of the following: complete remission without minimal residual disease (CRMRD-), complete remission (CR), CR with incomplete recovery (CRi), or morphological leukemia-free state (MLFS), or partial remission (PR) (all according to the 2017 European Leukemia Net (ELN) criteria (Döhner et al, 2017)      Duration of response	
•	Evaluate the pharmacokinetics (PK) of AMG 330 when AMG 330 and pembrolizumab are administered in combination	AMG 330 concentrations and PK parameters (eg: half-life, steady state concentration, volume of distribution, and clearance)	
•	Evaluate the immunogenicity of AMG 330 when administered in combination with pembrolizumab	Anti-AMG 330 antibody formation	

Protocol Number: 20170646

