### Fridericia-corrected QT Interval (QTcF)

The Fridericia correction will be calculated from the investigator reported QT (msec) and RR interval (msec), as follows: QTcF=QT/ (RR/1000)1/3

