### Baseline and Post-baseline ECG Values in Triplicate

The baseline ECG is defined as the mean of all pre-dose on cycle 1 day 1 assessments; the mean of values in a triplicate should be calculated before taking the mean of the triplicate averages.

For all post-baseline ECG, the mean value for measurements taken at the same assessment will be calculated and used in the analysis.

For post dose ECG measurements, unscheduled ECG measurements taken up to 5 minutes after the last assessments of a triplicate will be included in the average for a time point. When an ECG is missing within a triplicate, all available data will be averaged for that time point.

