#### 9.6.6 Electrocardiogram

All on-study electrocardiogram (ECG) data parameter (QRS, QT, QTc, RR, and PR intervals) will be listed and during the analysis one or all of these parameters will be plotted.

Summaries over time and/or changes from baseline over time will be provided for all ECG parameters. Subjects' maximum change from baseline in QTc will be categorized and the number and percentage of subjects in each group will be summarized. Subjects' maximum post baseline values will also be categorized and the number and percentage of subjects in each group will be summarized.

Summaries over time and/or changes from baseline over time will be provided for all 12-lead ECG parameters. The analysis of Fridericia's (QTcF) QT correction and Bazett's (QTcB) QT correction will be performed using the derived results as specified in Section 5.2.

Protocol Number: 20170646

**Date:** 25 August 2020 Page 23 of 35

Subjects will be categorized into the following groups per their maximum change from baseline in QTcF and QTcB. Unscheduled assessments will be included in the determination of the maximum change.

- ≤ 30 msec
- > 30 60 msec
- > 60 msec

The number and percentage of subjects in each group will be summarized. A listing of the subjects with > 60 msec change from baseline in QTcF and QTcB will be provided.

Subjects will also be categorized into the following groups per their maximum post baseline QTcF and QTcB. Unscheduled assessments will be included in the determination of the maximum post baseline value.

- ≤ 450 msec
- > 450 480 msec
- > 480 500 msec
- > 500 msec

The number of subjects in each group will be summarized for each dosing group. A listing of the subjects with > 500 msec post baseline in QTcF and QTcB will be provided.

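### The SAP computes QTcB and QTcF from investigator-reported QT and RR and makes no use of the central ECG read that the protocol arranges

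*SAP*

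**What the plan says.** Protocol Section 8.2.4.2 gives ECGs two destinations. At the site, "The investigator or designated site physician will review all ECGs". Separately, "ECGs will be transferred electronically to an ECG central reader for analysis per Amgen instructions". The same section asks for three baseline triplicates (nine ECGs) and a triplicate at each time point after dosing.

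SAP Section 5.1 fixes the inputs to both corrected intervals. QTcB is "calculated from the investigator reported QT (msec) and RR interval (msec", and for QTcF, "The Fridericia correction will be calculated from the investigator reported QT (msec) and RR interval (msec". SAP Section 5.2 then sets the averaging. At baseline, "the mean of values in a triplicate should be calculated before taking the mean of the triplicate averages", and after baseline the ECGs of one assessment are averaged.

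SAP Section 9.6.6 states that the QTcF and QTcB analysis "will be performed using the derived results as specified in" Section 5.2. It continues: "Subjects will be categorized into the following groups per their maximum change from baseline in QTcF and QTcB", with cut-points at 30 and 60 msec. Unscheduled assessments count towards the maximum. Maximum post-baseline values are also grouped, and subjects with a change above 60 msec or a value above 500 msec are listed.

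SAP Section 2.1 places ECG change in the primary safety endpoint, as part of "changes in vital signs, electrocardiograms (ECGs), and clinical laboratory tests". SAP Section 10 reports no changes from the protocol's analyses.

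**The concern.** The protocol arranges a central read and states its purpose as analysis. The SAP names a different source for the one ECG quantity that it categorises and lists. As written, the central read feeds no analysis that the SAP describes, and Section 10 does not present this as a departure.

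Two things are at stake. First, if site and central values differ for a subject, the documents do not say why the site value should populate the table or what the central value is for. The source could then be reconsidered after the data have been seen. Second, the main summary is each subject's maximum change, and a maximum tends to rise with measurement error even when nothing has changed. With about 20 subjects (Protocol Section 9.2), one subject moving between categories shifts a percentage by 1/20 = 5 points.

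**Working it through.** The plan has no figure to reproduce here. Neither document states reader variability or an expected number of QTc outliers, so the main check is a comparison of the texts.

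**Side by side**

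- Source for QT and RR: Protocol 8.2.4.2 has ECGs centrally read for analysis, while SAP 5.1 uses investigator-reported values for both corrections.
- Role of the site: Protocol 8.2.4.2 describes it as review, while SAP 5.1 makes it the supplier of the analysed intervals.
- Analysis section: Protocol 9.4.2.3.6 plans ECG summaries and QTc categories but names no source. SAP 9.6.6 uses the SAP-derived values.
- Declaration: SAP 10 reports no change.

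The passages in Protocol 8.2.4.2 and SAP 5.1 are intact, so redaction does not explain the difference. It applies to QTcF and QTcB alike.

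**Where measurement error would show**

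This part is illustration only. Assumptions: no true change, read-error SD *s* per ECG of 5 to 20 msec, and 4 or 8 post-baseline time points. None of these comes from the documents. The averaging of 9 baseline and 3 post-dose ECGs does.

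- Errors independent between ECGs: SD of change = *s*·√(1/9 + 1/3). At *s* = 15 this is 10.0 msec.
- Error shared within a triplicate: SD of change = *s*·√(1/3 + 1). At *s* = 15 this is 17.3 msec.

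Chance per subject that read error alone puts the maximum change over the threshold (400,000 simulated subjects; ranges run from 4 to 8 time points):

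| *s* (msec) | Independent, >30 | Independent, >60 | Shared, >30 | Shared, >60 |
|---|---|---|---|---|
| 5 | about 0 | about 0 | about 0 | about 0 |
| 10 | about 0 | about 0 | 1.8–3.4% | about 0 |
| 15 | 0.5–1.0% | about 0 | 14.3–24.2% | 0.10–0.20% |
| 20 | 4.5–8.3% | about 0.002% | 29.6–45.5% | 1.8–3.4% |

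The range above 30 msec runs from nothing to nearly half of subjects, depending on an error size and a correlation that the documents do not give. No row can be assigned to site or central reading, so the table does not compare the two. It supports one ordering only: the 30 msec threshold is far more sensitive to read error than the 60 msec threshold.

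**The case against.** The best case for leaving the SAP alone has four parts.

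- The protocol does not say that the central read is the value to be analysed. The transfer follows sponsor instructions that are not in the documents, and the word covering all ECGs belongs to the site review. Protocol 8.2.5.1.5 also has safety endpoints, ECG changes among them, reported on the Event CRF, which is an investigator route.
- A reader might infer that site reads are the noisier source and that several of the 20 subjects would be falsely shifted. The documents do not support this. They give no variability for either reader, and averaging over triplicates dampens independent error.
- The consequence is limited. ECG change is one descriptive item in a list of safety endpoints, no hypothesis is tested, and the decision on opening cohort 2 counts DLTs, not QTc categories. Subjects above 60 msec change or 500 msec are listed individually and can be checked.
- The protocol describes ECGs going to the reader, not a dataset coming back.

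The second and third parts stand, and they remove any claim about size. The first weakens the word conflict but does not explain why a read obtained for analysis appears in no analysis. The fourth is a practical matter to confirm. Protocol Section 11.3 provides, in general terms, for central data to reach the sponsor electronically.

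**Conclusion.** The mismatch is real. It covers both QT corrections and is neither explained nor declared. It goes beyond missing detail, because the SAP names a source that bypasses the read the protocol arranges. This rests on taking the stated purpose of the central transfer at its natural meaning, and on the SAP text available.

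Its size cannot be stated. It would be wrong to conclude from these documents that the chosen source is noisier, or that the category above 60 msec is materially inflated. If measurement error matters, it would act mainly on maximum changes above 30 msec. No error rate, sample size or cohort decision is affected.

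**What to change.** In SAP Sections 5.1 and 9.6.6, derive QTcF and QTcB from the central reader's QT and RR. Use investigator-reported values only where no central read exists, and flag them in the tables and listings.

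If the sponsor prefers investigator values as primary, declare this in SAP Section 10 with a reason and state how the central read will be used.

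While editing, correct the cross-reference in SAP Section 9.6.6: the QTc formulas are in Section 5.1, and Section 5.2 holds the averaging rules.

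The cost is SAP wording and use of the central read data. The sponsor should confirm that the reader's intervals come back as analysable data. Subjects need no new procedure, because the protocol already plans the ECGs and the transfer.

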### Fridericia-corrected QT Interval (QTcF)

The Fridericia correction will be calculated from the investigator reported QT (msec) and RR interval (msec), as follows: QTcF=QT/ (RR/1000)1/3

## 5.2 Study Points of Reference

## **Baseline**

For any variable, unless otherwise specified the baseline is the last assessment taken prior to the first administration of any IP. For parameters/assessments not scheduled to be performed (or scheduled but not performed) on the same day as the first administration of any IP, the baseline value is the value from the screening period measured closest to the day of first administration of any IP.

### Baseline and Post-baseline ECG Values in Triplicate

The baseline ECG is defined as the mean of all pre-dose on cycle 1 day 1 assessments; the mean of values in a triplicate should be calculated before taking the mean of the triplicate averages.

For all post-baseline ECG, the mean value for measurements taken at the same assessment will be calculated and used in the analysis.

For post dose ECG measurements, unscheduled ECG measurements taken up to 5 minutes after the last assessments of a triplicate will be included in the average for a time point. When an ECG is missing within a triplicate, all available data will be averaged for that time point.

### Change from Baseline

Change from baseline is the arithmetic difference between post-dose assessment and baseline.

Protocol Number: 20170646

Date: 25 August 2020 Page 15 of 35

Change (absolute) from Baseline = (Post-baseline Value – Baseline Value)

## Percent Change from Baseline

Change (percent) from Baseline = [(Post-baseline Value - Baseline Value)/Baseline

Value] x 100

## 5.3 Study Dates

#### Informed Consent Date

The date on which the subject signs the informed consent form.

### End of Study (primary completion)

The primary completion date is defined as the date when the last subject is assessed or receives an intervention for the final collection of data for the primary endpoint(s). If the study concludes prior to the primary completion date originally planned in the protocol (ie, early termination of the study), then the primary completion will be the date when the last subject is assessed or receives an intervention for evaluation in the study (ie, last subject last visit).

### End of Study

The end of study date is defined as the date when the last subject across all sites is assessed or receives an intervention for evaluation in the study (ie, last subject last visit), following any additional parts in the study (eg, additional antibody testing), as applicable.

#### End of Investigational Product (IP) Administration Date

End of IP Administration for each subject is defined as the date of decision was made to end IP reported on the End of IP Administration CRF page.

### **Enrollment Date**

A subject's enrollment date is defined as the date the investigator has determined he or she has met all eligibility criteria, as defined by the "Date of Enrollment" field on the Subject Enrollment form on the CRF.

### Last Dose Date of AMG 330 / Pembrolizumab

This is the stop date of the last infusion of AMG 330/pembrolizumab administration reported on the Investigational Product Administration CRF.

Protocol Number: 20170646

**Date:** 25 August 2020 Page 16 of 35

#### **Death Date**

For subjects who die during the study, the death date will be recorded on the end of study, event and survival status CRF. The earliest date will be used if the dates are inconsistent among these CRF pages.

#### Study Day 1

Study Day 1 is defined as the first day that investigational product is administered to the subject.

### Study Day:

Study Day is defined as:

Pre study day 1: study day = (date – date of study day 1)

Post study day 1: study day = (date - date of study day 1) + 1

# 5.4 Endpoints

### Treatment-emergent Adverse Event (TEAE)

Treatment emergent adverse event refers to an adverse event that starts on or after first dose of any IP (as indicated by the flag whether an event starts before first dose of any IP is "No" or missing on the Events CRF page) and up to and including end of study date. This reporting window also applies to treatment-emergent serious adverse events (SAEs).

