8.2.5.1.2 Serious Adverse Events

The investigator is responsible for ensuring that all serious adverse events observed by the investigator or reported by the subject that occur after signing of the informed consent through safety follow-up visit or 90 days following cessation of study treatment, (30 days following cessation of study treatment if the subject initiates new anticancer therapy), whichever is later, are reported using the Event CRF.

All serious adverse events will be collected, recorded and reported to the sponsor or designee within 24 hours of the investigator's knowledge of the event, as indicated in [Section 11.4](#). The investigator will submit any updated serious adverse event data to the sponsor within 24 hours of it being available.

The criteria for grade 4 in the CTCAE v5 grading scale differs from the regulatory criteria for serious adverse events. It is left to the investigator's judgment to report these grade 4 abnormalities as serious adverse events.

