Examples of such events include invasive or malignant cancers, intensive treatment in an emergency room or at home for allergic bronchospasm, blood dyscrasias or convulsions that do not result in hospitalization, or development of drug dependency or drug abuse.

Recording Adverse Events and Serious Adverse Events

Adverse Event and Serious Adverse Event Recording

- When an adverse event or serious adverse event occurs, it is the responsibility of the investigator to review all documentation (eg, hospital progress notes, laboratory, and diagnostics reports) related to the event.
- The investigator will then record all relevant adverse event/serious adverse event information in the Event case report form (CRF).
- The investigator must assign the following adverse event attributes:
 - Adverse event diagnosis or syndrome(s), if known (if not known, signs or symptoms);
 - Dates of onset and resolution (if resolved);
 - Severity (or toxicity defined below);
 - Assessment of relatedness to investigational product, other protocol-required therapies and
 - Action taken.
- If the severity of an adverse event changes from the date of onset to the date of resolution, record as a single event with the worst severity on the Event CRF.
- It is not acceptable for the investigator to send photocopies of the subject's medical records to sponsor in lieu of completion of the Event CRF page.
- If specifically requested, the investigator may need to provide additional follow-up information, such as discharge summaries, medical records, or extracts from the medical records. In this case, all subject identifiers, with the exception of the subject number, will be blinded on the copies of the medical records before submission to Amgen.
- The investigator will attempt to establish a diagnosis of the event based on signs, symptoms, and/or other clinical information. In such cases, the diagnosis (not the individual signs/symptoms) will be documented as the adverse event/serious adverse event.

Approved

Evaluating Adverse Events and Serious Adverse Events

Assessment of Severity

The investigator will make an assessment of severity for each adverse event and serious adverse event reported during the study. The assessment of severity will be based on:

The **Common Terminology Criteria for Adverse Events (CTCAE)**, version 5.0

which is available at the following location:

http://ctep.cancer.gov/protocolDevelopment/electronic_applications/ctc.htm.

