#### Treatment-related Adverse Event (TRAE)

A treatment-related AE is any treatment-emergent AE that per investigator review has a reasonable possibility of being caused by the investigational product (either AMG 330 or pembrolizumab or in combination of AMG 330 and pembrolizumab).

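### The SAP's treatment-emergent definition has no worsening clause, so a screening SAE that worsens after dosing is left out of the TEAE and TRAE tables

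*SAP*

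**What the plan says.** Protocol Appendix 4 leaves the definition of a TEAE to the SAP, so SAP Section 5.4 is the only definition. There, a TEAE "refers to an adverse event that starts on or after first dose of any IP", up to and including the end of study date. It is identified by whether "the flag whether an event starts before first dose of any IP is" answered No or missing on the Events CRF. The same window is applied to treatment-emergent SAEs.

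The SAP builds the treatment-related category on top of this: "A treatment-related AE is any treatment-emergent AE that per investigator review has a reasonable possibility of being caused by the investigational product".

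Two protocol rules decide what reaches that definition. Section 8.2.5.1.2 collects SAEs "that occur after signing of the informed consent through safety follow-up visit or 90 days following cessation of study treatment" (shortened if new anticancer therapy begins), while Section 8.2.5.1.1 collects non-serious events only from first dose. Appendix 4 then covers events that change: "If the severity of an adverse event changes from the date of onset to the date of resolution", the site enters a single event with the worst severity. The same appendix also lists exacerbation of a pre-existing condition, in frequency or intensity, as meeting the definition of an adverse event.

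For the tables, SAP Section 9.6.2 lists all TEAEs, TRAEs, SAEs, grade 3 and above events, events leading to withdrawal of product, and fatal events. It does not say whether the limit to treatment-emergent events applies to the later items. Protocol Section 9.4.2.3.2 names the fatal and serious event tables without any such limit.

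**The concern.** Safety is the primary objective, and TEAEs and TRAEs are primary endpoints. A definition that looks only at the start date treats an event that began before dosing as background, whatever happens to it afterwards. In these cases the error runs one way: it can only remove worsening on treatment from the TEAE and TRAE tables.

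The situation is plausible here. Protocol Appendix 8 lists febrile neutropenia, infections and sepsis as serious events expected in this population regardless of study drug. Section 2.3 expects neutropenia, and allows for infections, from the way AMG 330 works. Section 4.3 reports treatment-related febrile neutropenia in 22.4% of subjects in the monotherapy study. So the kinds of event that may be present at screening are also kinds that the drug may aggravate.

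**Working it through.** No figure in the plan is at issue. The check is to follow one case through the rules, then to size it.

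**The case.** A subject has an SAE in screening (at most 14 days), is still eligible, and receives study drug. The event is ongoing at first dose and then worsens, and the investigator judges the worsening related.

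1. *Is it in the database?* Yes. SAEs are collected from consent, and the sample SAE form in Appendix 4 has a box for events that occurred before first dose.
2. *Is the subject analysed?* Yes. The Safety Analysis Set is all enrolled subjects with at least 1 dose of either product (SAP 6.1).
3. *What start date does the event carry?* Under the single-record rule there is one event with one onset date, which is before dosing. The attributes that Appendix 4 requires are diagnosis, onset and resolution dates, severity, relatedness and action taken. A date of worsening is not among them.
4. *Classification.* The start-before-dose flag is Yes, so the event is not a TEAE. TRAE means TEAE and related, so it is not a TRAE either.

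| | One record, pre-dose start | Worsening entered as a new event |
|---|---|---|
| TEAE | no | yes |
| TRAE (judged related) | no | yes |
| SAE, grade 3 and above, or fatal table, where the event qualifies, if limited to TEAEs | no | yes |
| The same tables if not limited | yes | yes |

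The second column is what happens if a site follows the exacerbation item in Appendix 4 instead. Two sites could therefore classify the same case in opposite ways.

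**Size in a single row.** The tables count subjects. The planned enrolment is about 20, with at least 10 in cohort 1. One affected subject with no other event in that row is:

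- overall: 1/20 = 5 points. The exact 80% interval moves from 0 to 10.9% (0/20) to 0.5 to 18.1% (1/20).
- in a cohort of 10: 1/10 = 10 points. The interval moves from 0 to 20.6% (0/10) to 1.0 to 33.7% (1/10).

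The 80% level is the one that the SAP uses for response. It is borrowed here only for illustration.

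**Size in the any-TEAE and any-TRAE rows.** A subject is lost from these rows only if there is no other qualifying event. Protocol Section 4.3 reports TEAEs in 47/49 = 95.9% and AMG 330-related events in 43/49 = 87.8% of monotherapy subjects. Assuming that those rates hold here and are independent of the screening SAE, the expected loss from one affected subject is:

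- any TEAE: 5 × (1 − 0.959) = 0.2 points of 20 subjects; 10 × 0.041 = 0.4 points of 10.
- any TRAE: 5 × (1 − 0.878) = 0.6 points of 20 subjects; 10 × 0.122 = 1.2 points of 10.

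**The case against.** The strongest reply is that Appendix 4 already gives a route. Exacerbation of a pre-existing condition is an adverse event in its own right, so a site may enter the worsening as a new event with a post-dose start, and it is then a TEAE. The single-record rule can be read as covering only changes within one event. This stands in part: the documents are ambiguous and do not dictate one outcome. But for an event already recorded as an SAE and not yet resolved, the single-record rule is the more specific instruction. Nothing in the SAP settles which rule applies.

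The reply is also right that the case is rare. It needs an SAE within a short screening period that leaves the subject eligible, despite the exclusions for active infection needing IV antibiotics within 1 week, for significant cardiovascular risk and for other disorders that pose a risk. A new diagnosis after dosing, such as cytokine release syndrome, has its own record and is unaffected. A missing start flag counts as treatment-emergent, which errs towards inclusion.

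A reader might infer more than the documents support:

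- *That a fatal worsening disappears from the fatal-event table.* Neither SAP 9.6.2 nor Protocol 9.4.2.3.2 limits that table to TEAEs. The SAP 5.4 sentence on treatment-emergent SAEs makes a limit possible but does not state one.
- *That overall TEAE or TRAE incidence is understated by 5 or 10 points.* Most subjects are likely to have another qualifying event, so figures of that size belong to individual rows.
- *That the decision to open cohort 2 is affected.* DLTs are defined by occurrence in the DLT window, not by TEAE status. Reporting of SAEs to the sponsor is also unaffected.

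**Conclusion.** The point holds as a gap in a definition, with limited effect. With entry by start date alone, the single-record rule and TRAEs nested within TEAEs, a screening SAE that worsens after dosing is left out of the TEAE and TRAE tables, whatever the attribution. The exacerbation item in Appendix 4 means that sites may not handle such cases alike. Whether the SAE, grade 3 and above, and fatal tables lose the event is unclear from the text.

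The effect is confined to SAEs that start before dosing in subjects who are then dosed, and the documents do not say how many to expect. It would show mainly in preferred-term, worst-grade or rare-event rows, with little change in overall incidence. This rests on reading the single-record rule as keeping the pre-dose onset date, and on SAP Appendix A holding no worsening rule. That appendix is not in the public text; SAP 8.3 cites it only for incomplete adverse event and concomitant medication dates.

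**What to change.** - **SAP 5.4:** extend the TEAE definition with words such as: or that starts before first dose of any IP and worsens in grade, or becomes fatal, on or after first dose.
- **Protocol Appendix 4 and CRF instructions:** add an exception to the single-record rule, so that such worsening is entered as a new event dated at the worsening, and reconcile this with the exacerbation item. The SAP sentence alone is not enough, because the required event attributes include no date of worsening. The new record has a post-dose start, so the existing flag classifies it correctly. Since the tables count subjects, the second record does not count the same subject twice within a row.
- **SAP 9.6.2:** state whether the SAE, grade 3 and above, and fatal tables are limited to treatment-emergent events.

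The cost is a short protocol and CRF clarification, one added sentence in SAP 5.4 and a statement in 9.6.2. Event counts may rise slightly.
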